## **13 Ethical considerations and administrative procedures**

### **13.1 Regulatory and ethical compliance**

This clinical study was designed and shall be implemented, executed and reported in accordance with the ICH Harmonized Tripartite Guidelines for Good Clinical Practice, with applicable local regulations (including European Directive 2001/20/EC, US CFR 21), and with the ethical principles laid down in the Declaration of Helsinki.

### **13.2 Responsibilities of the investigator and IRB/IEC**

Before initiating a trial, the investigator/institution must obtain approval/favorable opinion from the Institutional Review Board/Independent Ethics Committee (IRB/IEC) for the trial protocol, written informed consent form, consent form updates, participant recruitment procedures (e.g., advertisements) and any other written information to be provided to participants. Prior to study start, the investigator is required to sign a protocol signature page confirming his/her agreement to conduct the study in accordance with these documents and all of the instructions and procedures found in this protocol and to give access to all relevant data and records to Novartis monitors, auditors, Novartis Quality Assurance representatives, designated agents of Novartis, IRBs/IECs, and regulatory authorities as required. If an inspection of the clinical site is requested by a regulatory authority, the investigator must inform Novartis immediately that this request has been made.

### **13.3 Publication of study protocol and results**

The protocol will be registered in a publicly accessible database such as [clinicaltrials.gov](http://clinicaltrials.gov) and as required in EudraCT. In addition, after study completion (defined as last patient last visit) and finalization of the study report the results of this trial will be submitted for publication and posted in a publicly accessible database of clinical trial results, such as the Novartis clinical trial results website and all required Health Authority websites (e.g. [Clinicaltrials.gov](http://Clinicaltrials.gov), [EudraCT](http://EudraCT) etc.) .

For details on the Novartis publication policy including authorship criteria, please refer to the Novartis publication policy training materials that were provided to you at the trial investigator meetings.

### **13.4 Quality Control and Quality Assurance**

Novartis maintains a robust Quality Management System (QMS) that includes all activities involved in quality assurance and quality control, to ensure compliance with written Standard Operating Procedures as well as applicable global/local GCP regulations and ICH Guidelines.

Audits of investigator sites, vendors, and Novartis systems are performed by auditors, independent from those involved in conducting, monitoring or performing quality control of the clinical trial. The clinical audit process uses a knowledge/risk based approach.

Audits are conducted to assess GCP compliance with global and local regulatory requirements, protocols and internal SOPs, and are performed according to written Novartis processes.

## **14 Protocol adherence**

This protocol defines the study objectives, the study procedures and the data to be collected on study participants. Additional assessments required to ensure safety of participants should be administered as deemed necessary on a case by case basis. Under no circumstances including incidental collection is an investigator allowed to collect additional data or conduct any additional procedures for any purpose involving any study treatment drugs under the protocol, other than the purpose of the study. If despite this interdiction prohibition, data, information, observation would be incidentally collected, the investigator shall immediately disclose it to Novartis and not use it for any purpose other than the study, except for the appropriate monitoring on study participants.

Investigators ascertain they will apply due diligence to avoid protocol deviations. If an investigator feels a protocol deviation would improve the conduct of the study this must be considered a protocol amendment, and unless such an amendment is agreed upon by Novartis and approved by the IRB/IEC and Health Authorities, where required, it cannot be implemented.

### **14.1 Protocol amendments**

Any change or addition to the protocol can only be made in a written protocol amendment that must be approved by Novartis, health authorities where required, and the IRB/IEC prior to implementation.

Only amendments that are required for participant safety may be implemented immediately provided the health authorities are subsequently notified by protocol amendment and the reviewing IRB/IEC is notified.

Notwithstanding the need for approval of formal protocol amendments, the investigator is expected to take any immediate action required for the safety of any participant included in this study, even if this action represents a deviation from the protocol. In such cases, Novartis should be notified of this action and the IRB/IEC at the study site should be informed according to local regulations.

## 16 Appendices

### 16.1 Appendix 1: Clinically notable laboratory values and vital signs

The following other specific criteria have been identified for this study:

Platelets < 75 000/ $\mu$ L

· Any patient who have platelets < 75 000/ $\mu$ L after being randomized should discontinue study treatment.

For all other laboratory assessments, the Central Laboratory will flag laboratory values falling outside of the normal ranges on the Central Laboratory Report (which the investigator should review and sign-off) and the investigator will report any values considered clinically significant in the eCRF.

Notable values for vital signs and change from baseline will be summarized.

Notable values for adults are defined as follows:

- heart rate of < 60 and > 100 bpm
- systolic blood pressure of < 90 and  $\geq$  140 mmHg
- diastolic blood pressure of < 60 and  $\geq$  90 mmHg

For ECGs a notable QTc value is defined as a QTcF interval of greater than 450 ms for males or greater than 460 ms for females - all such ECGs will be flagged by the Central CRO's cardiologist and require assessment for clinical relevance by the investigator. For adolescent participants, the Central CRO will use age-and gender-specific reference values.

Appendix 1.1: Clinically notable vital signs - adolescent participants

Guideline for pediatric blood pressure measurements:

**Table 16-1 Best Blood Pressure (BP) Measurement Practices - Pediatrics**

1. The child should be seated in a quiet room for 3-5 min before measurement, with the back supported and feet uncrossed on the floor.
2. BP should be measured in the right arm for consistency, for comparison with standard tables, and to avoid a falsely low reading from the left arm in the case of coarctation of the aorta. The arm should be at heart level, supported, and uncovered above the cuff. The patient and observer should not speak while the measurement is being taken.
3. The correct cuff size should be used. The bladder length should be 80%-100% of the circumference of the arm, and the width should be at least 40%.
4. For an auscultatory BP, the bell of the stethoscope should be placed over the brachial artery in the antecubital fossa, and the lower end of the cuff should be 2-3 cm above the antecubital fossa. The cuff should be inflated to 20-30 mm Hg above the point at which the radial pulse disappears. Overinflation should be avoided. The cuff should be deflated at a rate of 2-3 mm Hg per second. The first (phase I Korotkoff) and last (phase V Korotkoff) audible sounds should be taken as systolic blood pressure and diastolic blood pressure. If the Korotkoff sounds are heard to 0 mm Hg, the point at which the sound is muffled (phase IV Korotkoff) should be taken as the diastolic BP, or the measurement repeated with less pressure applied over the brachial artery. The measurement should be read to the nearest 2 mm Hg.
5. To measure BP in the legs, the patient should be in the prone position, if possible. An appropriately sized cuff should be placed midhigh and the stethoscope placed over the popliteal artery. The systolic BP in the legs is usually 10%-20% higher than the brachial artery pressure.

Adapted from [Pickering TG et al 2005](#)

**Table 16-2 Upper and lower limits for adolescents' vital signs that may be considered of concern if newly identified may be identified using the following table for guidance**

Age (Years)	Boys 		Girls 		Heart Rate 
	SBP (mm Hg)	DBP (mm Hg)	SBP (mm Hg)	DBP (mm Hg)	
12	>117	<75	>118	<75	62-96
13	>121	<75	>121	<76	
14	>126	<77	>122	<76	
15	>128	<79	>122	<77	60-92
16	>129	<80	>123	<77	
17	>131	<81	>124	<77	

The blood pressure values in the table above were adapted from [Flynn et al 2017](#) by modifying 5% of height (in table 6 of the publication) with 50% height to represent 'average' child height per age/sex. The normal values for vital signs in children vary greatly with age, growth and development. Selected BP threshold values serve as a representative guide of 'elevated BP' for a child of 'average' size.

The purpose of the values listed in this table is to guide investigators to identify or screen for values of concern in pediatric participants by age. The significance of these findings must be considered in view of the participant's disease, time course and overall clinical condition.

 Flynn JT, Kaelber DC, Baker-Smith CM, et al. Clinical practice guideline for screening and management of high blood pressure in children and adolescents

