**Table 8-4 Safety assessments**

Assessment	Specification
Physical examination	
A comprehensive physical examination will include the examination of general appearance, skin, neck (including thyroid), eyes, ears, nose, throat, lungs, heart, abdomen, back, lymph nodes, and extremities and vascular and neurological systems. If indicated based on medical history and/or symptoms, rectal, external genitalia, breast, and pelvic exams will be performed.
 
A short physical exam will include the examination of general appearance, vital signs and symptom-directed exams A short physical exam will be conducted at all visits except where a comprehensive physical examination is required (see Table 8-1).
 
Information for all physical examinations must be included in the source documentation at the study site. Clinically relevant findings that are present prior to signing informed consent must be recorded on the appropriate eCRF that captures medical history. Significant findings made after signing the informed consent which meet the definition of an AE must be recorded as an AE.

Vital signs	
Vital signs include blood pressure and pulse measurements. After the participant has been sitting for 5 minutes, with back supported and both feet placed on the floor, systolic and diastolic blood pressure will be measured 3 times using an automated validated device with an appropriately sized cuff. The repeat sitting measurements will be made at 1 - 2 minute intervals and the mean of the 3 measurements will be used. In case the cuff sizes available are not large enough for the participant's arm circumference, a sphygmomanometer with an appropriately sized cuff may be used.
 
Clinically notable vital signs are defined in Appendix 1.

---

Height and weight    Height in cm and Body weight (to the nearest 0.1 kg in indoor clothing, but without shoes) will be measured as specified in [Table 8-1](#).

---

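### Protocol Table 16-2 prints all 12 adolescent diastolic limits with a less-than sign, although its note says the thresholds mark elevated blood pressure

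*Protocol*

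**What the plan says.** Protocol Table 8-4, in the row on vital signs, says "Clinically notable vital signs are defined in" Appendix 1. Protocol Section 10.1.1 also refers to that appendix for alert ranges on laboratory and other tests. The numerical limits at the start of Appendix 1 are stated to be for adults, and they include "diastolic blood pressure of < 60 and" an upper limit of 90 mmHg or more.

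The adolescent part is Appendix 1.1, headed "Clinically notable vital signs - adolescent participants". It contains Table 16-2, whose title announces upper and lower limits for "vital signs that may be considered of concern if newly identified". Each row gives boys' systolic and diastolic limits and then girls'. The last row reads "17 >131 <81 >124 <77", and every other row has the same pattern of signs.

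The note below the table says the selected blood pressure thresholds are a "representative guide of 'elevated BP' for a child of 'average' size". It makes no exception for diastolic pressure. Footnote 1 names the source as a clinical practice "guideline for screening and management of high blood pressure in children and adolescents". The note also tempers the use of the table: "The significance of these findings must be considered in view of the participant's disease, time course and overall clinical condition".

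**The concern.** A threshold that marks elevated pressure has to be exceeded. The systolic columns follow that logic and the diastolic columns do the reverse, although the note describes both as one set of values from one source. An investigator who follows the table as printed would query ordinary adolescent diastolic readings and pass over raised ones.

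What is at stake is the site-level safety screen for participants aged 12 to 17. Table 16-2 is the only numerical vital-sign guidance that the protocol gives for them.

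**Working it through.** The plan states no figure to reproduce, so the check applies the table as printed and then with the signs reversed.

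**Inputs**
- Diastolic limits L from Table 16-2, ages 12 to 17: boys 75, 75, 77, 79, 80, 81; girls 75, 76, 76, 77, 77, 77.
- Adult low diastolic limit from Protocol Appendix 1: below 60.
- Adult high diastolic limit, which SAP Section 2.7.4.2 also applies to adolescents: 90 or more.

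**Step 1: count the signs.** Six ages by two sexes gives 12 cells per measure. Systolic cells with '>': 12 of 12. Diastolic cells with '<': 12 of 12.

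**Step 2: apply the limits to example diastolic readings.**

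| Reading (mmHg) | Cells flagged as printed | Cells flagged with '>' | Notable by adult limits |
|---|---|---|---|
| 55 | 12 of 12 | 0 of 12 | yes (low) |
| 65, 70, 74 | 12 of 12 | 0 of 12 | no |
| 85 | 0 of 12 | 12 of 12 | no |
| 90, 95 | 0 of 12 | 12 of 12 | yes (high) |

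Only the reversed signs agree with the note.

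**Step 3: find the range affected in each cell.**
- Flagged as printed, although neither elevated by the note nor low by the adult limit: 60 to L-1, which is L-60 whole-mmHg values.
- Raised, not flagged as printed, and below the SAP limit: L+1 to 89, which is 89-L values.

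| Age | Boys L | L-60 | 89-L | Girls L | L-60 | 89-L |
|---|---|---|---|---|---|---|
| 12 | 75 | 15 | 14 | 75 | 15 | 14 |
| 13 | 75 | 15 | 14 | 76 | 16 | 13 |
| 14 | 77 | 17 | 12 | 76 | 16 | 13 |
| 15 | 79 | 19 | 10 | 77 | 17 | 12 |
| 16 | 80 | 20 | 9 | 77 | 17 | 12 |
| 17 | 81 | 21 | 8 | 77 | 17 | 12 |

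The smallest L is 75, so 60-74 is flagged in all 12 cells; for boys aged 17 the range extends to 60-80. The largest L is 81, so readings of 82 and over are missed in all 12 cells. Below the SAP limit of 90, the missed range is 76-89 at age 12 and narrows to 82-89 for boys aged 17. A reading exactly equal to L is left out, because the documents do not settle '>' against '>='.

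**Step 4: test whether a lower limit could be intended.** A diastolic floor of 75 to 81 would sit 15 to 21 mmHg above the adult floor of 60 in the same appendix. It would also leave the table with no upper diastolic limit at all.

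**The case against.** The best textual defence is the table's title, which promises both upper and lower limits, so '<' might be a deliberate floor. That fails. The note speaks only of elevated pressure, the implied floor is far above the adult one, and the heart-rate column (62-96 and 60-92) already supplies lower limits. Reading '<' as marking the normal range does not help either. Each row would then mix abnormal systolic values with normal diastolic values, without a label, under a title about values of concern.

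A second defence is that the signs were corrupted when the text was taken from the PDF. The page image was not available, so this cannot be excluded. An error that changed every diastolic sign and spared every systolic one is unlikely.

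Several points limit the weight of the finding, and they stand:
- The title confines concern to newly identified values, so a reading already present at screening would not count.
- The 60 mmHg floor used for the over-flagged range is the adult one. The protocol gives no adolescent low diastolic limit.
- The mmHg counts describe the width of the affected range. They do not estimate how many participants would be affected, because no distribution of readings is given.
- The SAP listing is produced retrospectively and is no safety net during a visit.
- A clinician reading the note has the intended direction on the same page.

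**Conclusion.** The inconsistency is real: 12 of 12 diastolic limits contradict the table's own note and its stated source. It looks like a slip in the signs and not a chosen threshold.

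Its importance is low. The table is guidance subject to judgement, and no endpoint or discontinuation rule depends on it. The SAP listing of notable vital signs uses the adult limits for adolescents. Protocol Section 5 expected few adolescents and set no minimum number. SAP Section 1.1 reports 39 participants enrolled at termination, and the documents do not say how many were adolescents. With the trial stopped, the practical benefit is a correct record and a safe table if it is reused.

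The conclusion assumes that the extracted signs match the printed page.

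**What to change.** Change the 12 diastolic signs in Table 16-2 to '>' and keep the numbers. Confirm '>' against '>=' at the boundary in the cited high blood pressure guideline. The title could also be tidied: once corrected, the table gives upper limits only for blood pressure and a lower limit only for heart rate.

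The cost is one appendix table and one look at the source. The SAP, data collection and analysis need no change.

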## 16.2 Appendix 2: Liver event and laboratory trigger definitions & follow-up requirements

**Table 16-3 Liver event and laboratory trigger definitions**

	Definition/ threshold
Liver laboratory triggers If ALT, AST and total bilirubin normal at baseline:	
 
• ALT or AST > 5 × ULN
 
• ALP > 2 × ULN (in the absence of known bone pathology)
 
• Total bilirubin > 3 × ULN (in the absence of known Gilbert syndrome)
 
• ALT or AST > 3 × ULN and INR > 1.5
 
• Potential Hy's Law cases (defined as ALT or AST > 3 × ULN and Total bilirubin > 2 × ULN [mainly conjugated fraction] without notable increase in ALP to > 2 × ULN)
 
• Any clinical event of jaundice (or equivalent term)
 
• ALT or AST > 3 × ULN accompanied by (general) malaise, fatigue, abdominal pain, nausea, or vomiting, or rash with eosinophilia
 
• Any adverse event potentially indicative of a liver toxicity*
 

If ALT or AST abnormal at baseline:	ALT or AST > 3x baseline or > 300 U/L (whichever occurs first)
*These events cover the following: hepatic failure, fibrosis and cirrhosis, and other liver damage-related conditions; non-infectious hepatitis; benign, malignant and unspecified liver neoplasms ULN: upper limit of normal	

**Table 16-4 Follow up requirements for liver laboratory triggers – ALT, AST, TBL**

	ALT	TBL	Liver Symptoms	Action
ALT increase without bilirubin increase:				
	If normal at baseline: ALT > 3 x ULN  If elevated at baseline: ALT > 2 x baseline or > 300 U/L (whichever occurs first)	Normal For participants with Gilbert's syndrome: No change in baseline TBL	None	
 
• No change to study treatment
 
• Measure ALT, AST, ALP, GGT, TBIL, INR, albumin, CK, and GLDH in 48-72 hours.
 
• Follow-up for symptoms.
 

	ALT	TBL	Liver Symptoms	Action	
	
If normal at baseline: ALT > 5 x ULN for more than two weeks
 
If elevated at baseline: ALT > 3 x baseline or > 300 U/L (whichever occurs first) for more than two weeks
	
Normal
 
For participants with Gilbert's syndrome: No change in baseline TBL
	None	
 
• Interrupt study drug
 
• Measure ALT, AST, ALP, GGT, TBIL, INR, albumin, CK, and GLDH in 48-72 hours.
 
• Follow-up for symptoms.
 
• Initiate close monitoring and workup for competing etiologies.
 
• Study drug can be restarted only if another etiology is identified and liver enzymes return to baseline.
 
	
	
If normal at baseline: ALT > 8 x ULN
	Normal	None		
ALT increase with bilirubin increase:					
	
If normal at baseline: ALT > 3 x ULN
 
If elevated at baseline: ALT > 2 x baseline or > 300 U/L (whichever occurs first)
	
TBL > 2 x ULN (or INR > 1.5)
 
For participants with Gilbert's syndrome: Doubling of direct bilirubin
	None		
	
If normal at baseline: ALT > 3 x ULN
 
If elevated at baseline: ALT > 2 x baseline or > 300 U/L (whichever occurs first)
	Normal or elevated	Severe fatigue, nausea, vomiting, right upper quadrant pain		

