## **9 Discontinuation and completion**

### **9.1 Discontinuation from study treatment and from study**

#### **9.1.1 Discontinuation from study treatment**

Discontinuation of study treatment for a participant occurs when study treatment is permanently stopped for any reason (prior to the planned completion of study drug administration, if any) and can be initiated by either the participant or the investigator.

The investigator must discontinue study treatment for a given participant if the investigator believes that continuation would negatively impact the participant's well-being.

Discontinuation from study treatment is required under the following circumstances:

- Participant/guardian decision
- AEs for which continued exposure to the study drug would be detrimental
- Abnormal renal laboratory results requiring discontinuation (see [Appendix 3](#))
- Abnormal liver laboratory results requiring discontinuation (see [Appendix 2](#))
- Platelets < 75000/ $\mu$ L
- Pregnancy (see [Section 8.4.3](#) and [Section 10.1.4](#))
- Unblinding of study treatment other than to authorized personnel (see [Section 6.5](#)) for any reason
- Participant develops a medical condition that requires use of prohibited treatment as per [Section 6.2.2](#), or if participant exhibits a behavior of non-compliance regarding prohibited medications
- Participant received a live virus vaccination during the study
- Participant experiences an unexpected hypersensitivity reaction of grade 5, as defined by the World Allergy Organization Grading System ([Cox et al 2017](#)), see [Appendix 7](#):
- Emergency use of epinephrine due to anaphylactic or anaphylactoid reaction.
- Any other protocol deviation that results in a significant risk to the participant's safety
- Any situation in which study participation might result in a safety risk to the participant
- Following emergency unblinding

If 3 consecutive doses are missed (i.e a 12 week gap from last dose) a significant drop in drug exposure may be expected which can lead to aggravation of disease symptoms. Hence for the benefit of the participant, it is recommended that the participant be discontinued from the study treatment and avail of other alternative treatment options either in the follow up period or outside the study, as appropriate with participant condition.

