## 10.2 Additional Safety Monitoring

### 10.2.1 Liver safety monitoring

To ensure participant safety and enhance reliability in determining the hepatotoxic potential of an investigational drug, a standardized process for identification, monitoring and evaluation of liver events has to be followed.

Please refer to [Table 16-3](#) in [Appendix 2](#) for complete definitions of liver laboratory triggers.

Once a participant is exposed to study treatment, every liver event defined in [Table 16-3](#) should be followed up by the investigator or designated personnel at the trial site, as summarized below. Additional details on actions required in case of liver events are outlined in [Table 16.4](#) and [Table 16.5](#). Repeat liver chemistry tests (i.e. ALT, AST, TBL, PT/INR, ALP and G-GT) to confirm elevation.

- These liver chemistry repeats will be performed using the central laboratory. If results will not be available from the central laboratory, then the repeats can also be performed at a local laboratory to monitor the safety of the participant. If a liver event is subsequently reported, any local liver chemistry tests previously conducted that are associated with this event should have results recorded on the appropriate eCRF.
- If the initial elevation is confirmed, close observation of the participant will be initiated, including consideration of treatment interruption if deemed appropriate.
- Discontinuation of the study treatment ([Section 9.1.1](#)), if appropriate
- Hospitalization of the participant if appropriate
- Causality assessment of the liver event

- Thorough follow-up of the liver event should include
  - These investigations can include based on investigator’s discretion: serology tests, imaging and pathology assessments, hepatologist’s consultancy; obtaining more detailed history of symptoms and prior or concurrent diseases, history of concomitant drug use, exclusion of underlying liver disease

All follow-up information and procedures performed must be recorded as appropriate in the eCRF.

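### In protocol Table 16-4 the bilirubin/INR row and the symptom row are keyed to ALT only, so an AST-driven liver event that Table 16-3 defines can reach no mandatory drug interruption.

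*Protocol*

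**What the plan says.** **Triggers.** Protocol Appendix 2, Table 16-3, lists three triggers for participants with normal baseline that pair a transaminase above 3x ULN with a second sign. The second sign is INR above 1.5, total bilirubin above 2x ULN without a notable ALP rise, or symptoms. Each accepts either enzyme; the bilirubin entry begins "Potential Hy's Law cases (defined as ALT or AST". SAP section 5.5, Table 5-3, also uses either enzyme for its potential Hy's Law category.

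**Actions.** Table 16-4 is captioned "Follow up requirements for liver laboratory triggers – ALT, AST, TBL". Its enzyme column is headed ALT and every threshold in it is an ALT threshold. Apart from the caption, AST appears only among the tests to repeat. The block "ALT increase with bilirubin increase" holds the two rows that answer the combined triggers: one for bilirubin above 2x ULN or INR above 1.5, one for symptoms ("Severe fatigue, nausea, vomiting, right upper quadrant pain"). The action for the more serious rows is "Interrupt study drug", with restart only if another cause is found and enzymes are back to baseline.

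**General rules.** Section 10.2.1 sets its scope with "Once a participant is exposed to study treatment, every liver event defined in" Table 16-3, so AST-driven events are included. On confirmation it asks for "close observation of the participant will be initiated, including consideration of treatment interruption if deemed appropriate". Section 9.1.1 lists "Abnormal liver laboratory results requiring discontinuation" among the required reasons to stop, and for this item refers back to Appendix 2.

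**The concern.** The table that defines liver events and the table that says what to do about them use different enzyme criteria. Two participants with mirror-image findings, both labelled potential Hy's Law by the protocol, are handled differently according to which transaminase crosses 3x ULN. For one, the next four-weekly injection is withheld and restart has stated conditions. For the other, both decisions are left to the investigator. Because the SAP counts the case by either enzyme, the study report could show a potential Hy's Law case for which the protocol did not require interruption.

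**Working it through.** There is no sample-size or power figure to reproduce. The check follows each combined trigger through every place that sets an action, once driven by AST and once by ALT. Values are multiples of ULN, with normal baseline and ALP 1.0. The AST-driven case has AST 4.0 and ALT 2.5; the mirror swaps them. These values are illustrative and were chosen to satisfy the printed cut-offs.

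| Second sign | Table 16-3 trigger | Table 16-4 row, AST-driven | Table 16-4 row, ALT mirror |
|---|---|---|---|
| Bilirubin 2.5, mainly conjugated | Potential Hy's Law | None | Bilirubin/INR row |
| INR 1.7, bilirubin normal | INR | None | Bilirubin/INR row |
| Severe nausea and vomiting, bilirubin normal | Symptoms | None | Symptom row |

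The reason is the same each time: both rows need ALT above 3.0, and 2.5 does not exceed 3.0. Three of three combined triggers admit AST, and none of the two answering rows does. The three cases restate one wording difference; they show its reach, not how often it would arise.

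Next, whether another rule requires interruption for the AST-driven case:

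- **Table 16-4, normal-bilirubin rows.** These need ALT above 3, 5 or 8x ULN. Not met.
- **Table 16-5.** Its bilirubin rows are for an isolated rise. Read literally they do not apply, because AST is raised too. If a site applied them anyway, bilirubin of 2.5 falls in the 1.5 to 3.0 band, where treatment is maintained. Above 3 and up to 10 it would be interrupted, and above 10 discontinued.
- **Table 16-5, row for adverse events suggesting liver toxicity.** Interruption or discontinuation is to be considered, not required.
- **Section 10.2.1.** Repeat tests, observation, causality assessment and recording apply. Interruption and discontinuation are each qualified by appropriateness.
- **Section 9.1.1.** The liver item leads back to Appendix 2. The remaining relevant items cover adverse events where further exposure would be detrimental, situations that might put the participant at risk, and the investigator's belief that continuing would be harmful. They bind once judged to be met, but the judgement comes first.

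So the gap is fully open for bilirubin above 2 and up to 3x ULN, and for the INR and symptom triggers with bilirubin at or below 3x ULN. Above 3x ULN it depends on how a site reads the word isolated in Table 16-5.

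One input is a reading rather than printed text. In the text available, the action cells of the two rows are blank, and I take the interruption cell above them as merged down. Otherwise a raised ALT with raised bilirubin would carry no action, while ALT above 5x ULN for more than two weeks with normal bilirubin is interrupted. The laid-out table can confirm this.

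**The case against.** The strongest reply is that these cases are not neglected. Section 10.2.1 covers every Table 16-3 event whichever enzyme drives it, and four-weekly dosing leaves time to retest before the next injection. Section 9.1.1 makes stopping compulsory once the investigator judges that exposure would be detrimental or that there is a safety risk, and a confirmed potential Hy's Law case may well be judged so. The caption of Table 16-4 would also lead a site to look there for AST. All of this stands. It shows the case is managed, but not that interruption is required as it is for ALT.

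A second reply is that AST is less specific to the liver. That is a reason for care with the rows that rest on the enzyme alone. It does not answer the two rows at issue, which need a second sign and whose triggers already accept AST.

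Third, the SAP (sections 1.1 and 1.1.2) records that the study was terminated with 39 participants enrolled and that treatment was stopped. No dosing decision in this trial can now change. That reduces urgency; it does not make the tables agree.

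Stronger readings are tempting but unsupported. A reader might infer that no rule could ever stop treatment in an AST-driven case; Table 16-5 above 3x ULN bilirubin and the general items of section 9.1.1 prevent that claim. A reader might also infer a known liver hazard. Protocol section 4.5 does not list hepatotoxicity among the risks it describes, nor does SAP section 2.7.1.2 list it among events of special interest, and neither document says how often the AST-driven pattern occurs.

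**Conclusion.** The inconsistency is real and worth correcting. With normal baseline, AST above 3x ULN and ALT at or below 3x ULN, a participant with bilirubin above 2 and up to 3x ULN, INR above 1.5, or symptoms is a defined liver event for which interruption is left to judgement. The same pattern driven by ALT is interrupted by rule. Two assumptions carry this: that the interruption cell extends down to both rows, and that Table 16-5 is confined to isolated bilirubin rises as labelled. The finding concerns agreement between two tables of one appendix. It is not evidence that anyone was harmed. For this terminated trial it bears on how any reported case is read and on reuse of the appendix elsewhere.

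**What to change.** In the bilirubin/INR row and the symptom row of Table 16-4, replace ALT with ALT or AST, and change their block heading in the same way. The enzyme criterion then agrees with Table 16-3, and all three AST-driven cases above reach the same row as their ALT mirrors.

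The cost is a few words in one table. ALT, AST and total bilirubin are already in the chemistry panel (Table 8-5), and INR is in the repeat liver panel (section 10.2.1).

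This does not make the two tables agree in full. AST above 5x ULN alone would still have no action row. Malaise and rash with eosinophilia are triggers but are missing from the symptom row. The abnormal-baseline cut-offs also differ: 3x baseline in Table 16-3 against 2x baseline in these rows. Whether to extend AST to the normal-bilirubin rows is for the sponsor's hepatic safety experts; AST can come from muscle, and the table already asks for CK.
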